6.1 Subject Disposition, Completion Rate and Reasons for Discontinuation

Subject disposition will be summarized for the Randomized Sample by treatment group, and by center.

Subject completion rate and reasons for discontinuation will be summarized for the Randomized Sample by treatment group for the double-blind treatment period.

6.2 Treatment Compliance

For each subject, compliance in taking IMP is calculated by dividing the number of tablets taken by the total number of tablets the patients were scheduled to take during the double-blind

SAP 405-201-00013

treatment period. Compliance is calculated on double-blind IMP for the double-blind treatment period. For lost-to-follow up patients, the last IMP end date record will be used as the treatment end date.

Summary of Treatment compliance will be provided based on both eCRF data and AiCure captured data, respectively.

6.3 Protocol Deviation

Protocol deviations are summarized by center and type of deviation for randomized subjects by treatment group. Listing of protocol deviation will list the treatment phases during which the deviations occurred. In addition, protocol deviations affected by the COVID-19 will be summarized. Listing of subjects with protocol deviations affected by the COVID-19 will also be provided.

7 Baseline Characteristics

7.1 Baseline Definition

Baseline for the single-blind placebo run-in period refers to last available measurement prior to the start of administration of placebo in the single-blind placebo run-in period.

For analyses of the double-blind treatment period data, the baseline is defined as the last available measurement prior to the first dose of double-blind Investigational Medicinal Product (IMP) in the double-blind treatment period.

7.2 Demographic Characteristics

For the Randomized Sample, demographic characteristics will be summarized by treatment group. Age, race, ethnicity, height, weight, waist circumference, and body mass index (BMI) will be tabulated by gender and overall using the baseline assessments for the single-blind placebo run-in period.

Mean, range and standard deviation will be used to describe continuous variables such as age. Frequency distributions will be tabulated for categorical variables such as race.

7.3 Medical and Psychiatric History

A summary of medical and psychiatric history will be presented for the Randomized Sample by treatment group and overall.

A summary of the Adult ADHD Clinical Diagnostic Scale (ACDS) at screening will also be presented for the Randomized Sample (by treatment group and overall). The number and

SAP 405-201-00013

percentage of patients with each response to items A23-A41 from Section A (Childhood ADHD Symptoms Summary), B22-B39 from Section B (Adult ADHD Symptoms Summary), and C1-C5 will be presented.

7.4 Neuropsychiatric Diagnosis

A summary of MINI International Neuropsychiatric Interview (M.I.N.I.) will be presented for the Randomized Sample by treatment group and overall. Summarized will be the number and percentage of patients who meet each diagnosis criteria, and number and percentage of patients with each primary diagnosis.

7.5 Baseline Psychiatric Evaluation

For the Randomized Sample, baseline for the single-blind placebo run-in period and baseline for the double-blind treatment period psychiatric scale evaluation will be summarized by treatment group and overall. The mean, median, range and standard deviation will be used to summarize the assessments of: AISRS total score, ASRS and CGI - Severity of Illness Score (CGI-S).

8 Efficacy Analysis

All efficacy analyses pertaining to the double-blind treatment period will be performed on the Efficacy Sample, and patients will be included in the treatment group as randomized.

For analysis of the double-blind treatment period data, the baseline for the double-blind treatment period defined in [Section 7.1](#) will be used. Statistical comparisons are based on 2-sided, 0.05 significance levels.

8.1 Primary Efficacy Endpoint

The primary efficacy endpoint is the change from the baseline of the double-blind treatment period to Day 42 in AISRS total score.

8.1.1 Primary Efficacy Analysis

The objective of the primary efficacy analysis is to compare the efficacy between centanafadine (SR 200 mg TDD or SR 400 mg TDD) and placebo.

The primary estimand defining the treatment effect of interest in the trial uses the hypothetical strategy specified in the draft ICH E9 (R1) Addendum. The objective of the primary analysis is to evaluate the efficacy of centanafadine SR 400mg TDD in adult subjects with ADHD

SAP 405-201-00013

versus placebo. The estimand, or target of estimation, following the hypothetical strategy is the pharmacological effect seen, had no withdrawals occurred. This hypothetical estimand is justifiable in this case, since the focus is on the pharmacological effect of the drug additional to non-specific effects. Subjects who withdraw from a symptomatic IMP treatment either could have lost their treatment effect, had the subjects not taken any other symptomatic medication after withdrawal, or could have their treatment effect been masked, had the subjects taken other symptomatic medication after withdrawal. This means that any observations taken after subjects stop IMP will most likely not contribute relevant information about the pharmacological effect of the drug. Due to this strategy, the last collected efficacy assessment after premature trial discontinuation will be done only once at the ET Visit. Every effort will be made to complete all of the ET evaluations prior to administering any additional medications for the treatment of ADHD or other prohibited medications. In the case of terminal or lost to follow-up events, no ET evaluations would be expected, and only scheduled assessments performed before such an event has occurred.

The primary estimand for this trial is defined by the following components:

- Target Population: Efficacy Sample
- Endpoint: Change from baseline to Day 42 in the AISRS total score
- Intercurrent Events: Premature treatment discontinuation
- Measure of Intervention Effect: Difference in endpoint means between centanafadine (SR 200 mg TDD or SR 400 mg TDD) and placebo.

In this hypothetical strategy, the event of withdrawing IMP is considered missing at random (MAR), and the primary endpoint of the trial could be considered as a combination of the responses of on-treatment completers at Day 42 and the imputation of the endpoint to Day 42 following the trend in each treatment group using the MMRM method for subjects who withdraw IMP during the trial. All data collected during the trial treatment period will be used for statistical analysis. For the primary efficacy analysis, the treatment effect will be estimated using the MMRM method described below. Under the MAR assumption, MMRM provides an unbiased estimate of treatment effect for the treatment period. Analyses with missing values imputed by multiple imputation under MNAR and other methods will be performed as sensitivity analyses. The primary analysis will be performed on Efficacy Sample which includes all randomized subjects who took at least 1 dose of IMP in the double-blind treatment period and who have both a baseline for the double-blind treatment period and at least one post-randomization AISRS total score during the double-blind treatment period. The primary efficacy analysis will be performed by fitting a MMRM analysis with an unstructured (UN) variance covariance structure in which the change from baseline for the double-blind

SAP 405-201-00013

treatment period in AISRS total score at the scheduled double-blind treatment period visits will be the dependent variable based on the OC data set. The model will include fixed class effect terms for treatment, study center, visit day, and an interaction term of treatment by visit day. The model will also include the interaction term of baseline values for the double-blind treatment period of AISRS Total score by visit day as covariates. The primary comparison between centanafadine (400 mg TDD group or 200 mg TDD group) and placebo at Day 42 in the double-blind treatment period will be estimated as the difference between Least Squares (LS) means utilizing the computing software SAS procedure PROC MIXED.

In case there is a convergence problem with MMRM model with the unstructured (UN) variance covariance matrix, the following structures other than unstructured will be used in order of 1) heterogeneous toeplitz (TOEPH), 2) heterogeneous autoregressive of order 1 (ARH1), and 3) heterogeneous compound symmetry (CSH) and the first (co)variance structure converging to the best fit will be used as the primary analysis. If a structured covariance has to be used, the empirical “sandwich” estimator of the standard error of the fixed effects parameters will be used in order to deal with possible model misspecification of the covariance matrix.

Small centers will be defined as centers that do not have at least one evaluable subject (evaluable with regard to the primary efficacy variable) in each treatment arm in the double-blind treatment period. All small centers will be pooled to form “pseudo centers” for the purpose of analysis according to the following algorithm. Small centers will be ordered from the largest to the smallest based on the number of evaluable subjects (i.e., subjects who have baseline and at least one post-baseline value for the primary endpoint in the double-blind treatment period). The process will start by pooling the largest of the small centers with the smallest of the small centers until a non-small center is formed. This process will be repeated using the centers left out of the previous pass. In case of ties in center size, the center with the smallest center code will be selected. If any centers are left out at the end of this process, they will be pooled with the smallest pseudo centers, or if no pseudo centers exist, they will be pooled with the smallest non-small center.

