3.7.1.4.2 Visit 9/End of Treatment/Early Termination

The assessments described for Visit 9 (Day 42/early termination [ET]) in the Schedule of Assessments ([Table 3.7-1](#)) will be completed. If a subject discontinues early before Day 42, procedures noted for Day 42 must be completed at the ET visit. Attempts should be made to complete **ALL** evaluations, particularly efficacy assessments (ie, AISRS, CGI Change from Baseline, CGI-S, ASRS, and AIM-A), for the Day 42/ET visit prior to the administration of any new ADHD medications. However, if the subject receives a new ADHD medication or has a urine drug screen positive for any new ADHD medication prior to the conduct of ET procedures, no efficacy assessments should be performed.

Protocol 405-201-00013

The following should also be noted:

- Urine drug screen results from the previous visit will be reviewed. If the subject is positive for any new ADHD medication, no efficacy assessments should be conducted.
- Subjects will return their dosing card from the prior week, accountability, and compliance will be verified.
- Sparse PK sample will be collected.
- For all subjects who complete the trial (Section 3.10) and are considering entry into the open-label rollover trial, they will be instructed to refrain from utilizing prohibited concomitant medications (Section 4.1), including ADHD treatments, during the 7-day safety follow-up period. For subjects who early terminate or decline participation in the open-label trial, they will be instructed to refrain from utilizing prohibited concomitant medications (Section 4.1), including ADHD treatments, until after the follow-up telephone call 10 days after the last dose of IMP.
- For subjects who early terminate or decline participation in the open-label trial, future treatment options will be discussed, and subjects will complete follow-up visits and procedures described in Section 3.7.1.5 and Section 3.7.1.6.

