3.8.3 Individual Subject Discontinuation

3.8.3.1 Treatment Discontinuation

After randomization, a subject may stop treatment permanently for a variety of reasons. Treatment discontinuations may be initiated by a subject who is not satisfied with treatment or may become medically necessary due to AEs, required treatment with a disallowed medication or therapy, or other issues, as determined by the investigator. However, each investigator must comprehensively review the circumstances and offer the subject options for continued treatment to the degree possible as described in [Section 3.8.3.4](#). Refer to [Table 3.7-2](#) for a description of follow-up procedures.

A urine drug screen will be collected and sent to the central lab at the time points described [Table 3.7-1](#) and [Table 3.7-2](#). At the start of the single-blind placebo run-in period through the Day 42/ET visit, if the subject is tests positive for any prohibited medications (including medications for the treatment of ADHD, see [Section 4.1](#)), the subject will be early terminated, and the procedures outlined in [Section 3.7.1.4.2](#) will be completed.

At the baseline visit only, if subjects have a $\geq 30\%$ improvement in the ASRS (18 item) ADHD Symptoms score compared to the score at the start of the single-blind placebo run-in, they will be early terminated.

Protocol 405-201-00013

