3.10 Definition of Completed Subjects

The treatment period is defined as the time period during which subjects are evaluated for primary and secondary objectives of the trial irrespective of whether or not the subject actually consumed all doses of the IMP. Subjects who are evaluated at the last scheduled visit during the treatment period will be defined as trial completers. For purposes of this trial, subjects who complete the Day 42/ET visit will be defined as trial completers.

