7.3 Primary, Secondary, and Exploratory Endpoint Analyses

7.3.1 Primary Efficacy Endpoint Analysis

The objective of the primary efficacy analysis is to compare the efficacy between centanafadine (SR 200 mg TDD or SR 400 mg TDD) and placebo. The primary efficacy endpoint is the change from baseline to Day 42 in AISRS total score. For analysis of the double-blind treatment period data, baseline is defined as the last available measurement prior to the first dose of double-blind IMP in the double-blind treatment period.

The estimand for the primary efficacy analysis is the difference in outcome improvement if all subjects tolerated and adhered to their treatment. This approach is Estimand #3,

Protocol 405-201-00013

recommended by the 2010 National Academy of Sciences' National Research Council report on prevention and treatment of missing data and ICH E9 (R1) "Addendum to Statistical Principles for Clinical Trials on Choosing Appropriate Estimands and Defining Sensitivity Analyses in Clinical Trials".

This estimand focuses on the efficacy of centanafadine (SR 200 mg TDD or SR 400 mg TDD) in change from the baseline in AISRS total score. The objective of this trial is consistent with the election of an efficacy rather than effectiveness estimand.

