8.2 Key Secondary Efficacy Endpoint

The key secondary efficacy endpoint is the change from baseline of the double-blind treatment period to Day 42 using the CGI-S. This key secondary efficacy endpoint will be analyzed by fitting the same MMRM model described in the primary analysis.

To control the overall experiment-wise type I error at 0.05 level, A fixed sequence testing approach will be applied. The statistical test will be performed in the following order:

- 1) Change from baseline to Day 42 in the double-blind treatment period in AISRS total score between centanafadine 400 mg TDD and placebo;

SAP 405-201-00013

- 2) Change from baseline to Day 42 in the double-blind treatment period in AISRS total score between centanafadine 200 mg TDD and placebo;
- 3) Change from baseline to Day 42 in CGI-S score between centanafadine 400 mg TDD and placebo;
- 4) Change from baseline to Day 42 in CGI-S score between centanafadine 200 mg TDD and placebo.

The testing procedure will stop at the first comparison where the p-value is ≥ 0.05 . None of the subsequent comparisons will be performed.

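### AISRS and CGI-S ratings made at the visit of a urine sample later found positive for ADHD medication, including Day 42, stay in both MMRMs because the SAP does not address such use on treatment

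*SAP*

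**What the plan says.** **Timing of the screen.** Protocol 3.8.3.1: "A urine drug screen will be collected and sent to the central lab at the time points described". From the start of run-in through the Day 42/ET visit, "if the subject is tests positive for any prohibited medications", early termination follows. Protocol 3.7.1.4.1 (Visits 4 to 8) and 3.7.1.4.2 (Visit 9/ET) both have the site review the result of the previous visit's sample. Section 3.7.1.4.2 adds a bar on rating, which also covers known use of such a drug: if the subject "has a urine drug screen positive for any new ADHD medication prior to the conduct of ET procedures, no efficacy assessments should be performed". Completers are defined in Protocol 3.10: "For purposes of this trial, subjects who complete the Day 42/ET visit will be defined as trial completers".

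**Data analysed.** SAP 8.1.1: "All data collected during the trial treatment period will be used for statistical analysis". It describes the endpoint as a combination of "the responses of on-treatment completers at Day 42" and model-based values for those who stopped. The observed-cases set in SAP 5.2 holds every recorded observation in the double-blind period. SAP 10.1 removes only ratings more than three days after the last dose or in follow-up. For CGI-S, SAP 8.2 says: "This key secondary efficacy endpoint will be analyzed by fitting the same MMRM model described in the primary analysis".

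**Target.** Protocol 7.3.1: "The estimand for the primary efficacy analysis is the difference in outcome improvement if all subjects tolerated and adhered to their treatment". Protocol 7.3.2.1 sets the same estimand for CGI-S. SAP 8.1.1 lists one intercurrent event, premature treatment discontinuation, and discusses masking by other symptomatic medication only after withdrawal.

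**The concern.** Handling of a positive screen starts one visit late. The subject is terminated and, if the drug is a new ADHD medication, the ET efficacy ratings are not made. The rating from the visit of the positive sample is already in the database, and no rule takes it out.

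Day 42 is the sharpest case. Its own sample is read after the endpoint rating, the subject counts as a completer, and the value enters as an on-treatment response. If Protocol 3.8.3.1 makes that subject an early termination instead, a rating within three days of the last dose still stays.

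A rating made under another ADHD drug does not estimate the effect of centanafadine under adherence. An excess of such ratings on active treatment would inflate the difference, and an excess on placebo would shrink it. Both the primary and the key secondary endpoint are exposed, because they share the model.

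**Working it through.** **1. Path of one rating, documents side by side.**

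| Step | Source | Consequence |
|---|---|---|
| Sample and rating at the same visit; sample sent away | Protocol Table 3.7-1, 3.8.3.1 | No central result when the rating is made |
| Result reviewed at next visit | Protocol 3.7.1.4.1, 3.7.1.4.2 | Sampling-visit rating already recorded |
| Subject terminated; ET ratings barred if the drug is a new ADHD medication | Protocol 3.7.1.4.1, 3.7.1.4.2 | Later ratings stopped, earlier one untouched |
| All treatment-period data, observed cases | SAP 8.1.1, 5.2 | Rating kept |
| Exclusion only by time since last dose or follow-up | SAP 10.1 | A subject still dosing is not excluded |
| Same model for CGI-S | SAP 8.2 | Same result |

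**2. The plan's own figure.** Inputs from Protocol 7.1: difference 5, SD 12.5, 135 evaluable per arm, two-sided alpha 0.05.

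- SE = 12.5 × √(2/135) = 1.521.
- Noncentrality = 5/1.521 = 3.286, with 268 degrees of freedom.
- Power = 90.6% (noncentral t), which agrees with the stated minimum of 90%.
- 405/0.90 = 450 randomized, as stated.

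**3. Size at the planning values.** Assumed, not in the documents: a net excess of 2 affected Day 42 ratings in one arm, each shifted by 5 to 10 AISRS points, with the SE unchanged. Shift in the arm mean = number × points / 135.

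| Points per rating | Shift | Type I error if the excess is on active | Power if the excess is on placebo |
|---|---|---|---|
| 5 | 10/135 = 0.074 | 0.0503 | 89.7% (difference 4.926) |
| 10 | 20/135 = 0.148 | 0.0511 | 88.8% (difference 4.852) |

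With equal numbers and shifts in the two arms, the net shift is zero.

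**4. Ratings before Day 42.** When the affected rating is a subject's last, the model carries part of its shift into that subject's implied Day 42 value. The coefficient of the last rating, given all earlier ones, follows from the unstructured covariance matrix in output STAT-4.1.1: 0.735 (Day 7), 0.836 (Day 14), 0.832 (Day 21), 0.661 (Day 28) and 0.443 (Day 35). Earlier positives therefore also reach the endpoint, each with less weight than a Day 42 positive.

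**5. Existing checks.**

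- The Per Protocol Sample (SAP 5.1) drops subjects with reported use, or a logged major deviation, that affects the primary endpoint. It is a sensitivity analysis, and its only efficacy table (CT-5.2.1.2) is for AISRS.
- In SAP 8.1.3.1, the scenario treating all dropouts as MNAR includes these subjects. Its imputation starts from the affected rating, and no scenario changes an observed Day 42 value.

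**The case against.** The strongest reply is that nothing in the SAP is broken. Its estimand is the effect had no withdrawals occurred, its only intercurrent event is discontinuation, and its masking argument concerns medication taken after withdrawal. Adherence in the protocol estimand can be read as adherence to study drug alone. This stands in part. A reader might infer that the SAP sets a hypothetical strategy for concomitant ADHD medication and then violates it. The documents do not support that: use while on study drug is simply not addressed.

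A reader might also infer that keeping these ratings breaches Protocol 3.7.1.4.2. It does not. That rule sits in the Visit 9/ET section and covers use known before those ratings. Its evident purpose, to avoid ratings under other ADHD medication, is what the retained ratings run against.

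Recorded use that the urine panel would miss is largely a separate matter. The site knows of it, and the Per Protocol criterion on reported use is aimed at it.

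Screening before randomization and at every treatment visit limits the number of affected ratings. Using a sensitivity analysis for the rest is defensible, but the planned one depends on reported use or logged deviations and does not cover CGI-S.

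The remedy has weaknesses too. A positive sample does not date use, and a class result such as amphetamines does not by itself identify an ADHD medication. Removing ratings after a post-randomization event that may reflect poor response replaces data with a MAR assumption. The fix has to allow for each of these.

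**Conclusion.** The gap is real. Ratings from the visit of a positive sample, Day 42 included, stay in the AISRS and CGI-S models, and the SAP gives no handling for ADHD medication taken on treatment. They fit neither the protocol's adherence-based estimand nor the purpose of its bar on ET ratings.

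The number affected and the direction of bias are unknown. At the planning values the effect is small (type I error up to 0.0511, or power down to 88.8%), and even that rests on an assumed count and an assumed 5 to 10 points per rating.

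A reader who sees the outputs bound with the SAP might infer that the 400 mg result depends on such ratings. Its upper confidence limit is -0.1364, with 119 Day 42 ratings in that arm. Two net affected ratings at 10 points, or four at 5, would move the estimate by 20/119 = 0.168 and p from 0.0392 to 0.053. The documents do not support that inference: they report no positive screens, no imbalance between arms and no effect per rating. With a limit that close to zero, a few altered ratings of any kind could do the same. The observed limit should not be the reason for the change.

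This is a cheap improvement of low severity.

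**What to change.** In SAP 8.1.1 and 8.2:

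- Name documented use of prohibited ADHD medication during treatment as an intercurrent event under the hypothetical strategy. Documented means recorded use, or a urine screen positive for an ADHD medication after setting aside positives explained by another drug.
- Set AISRS and CGI-S to missing from the earlier of first documented use and the visit of the positive sample, including Day 42.
- Keep the all-data MMRM as a sensitivity analysis.
- Treat these subjects as MNAR in one scenario of SAP 8.1.3.1.
- Report the number of affected ratings by arm and visit. A count of zero would settle the question.

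The cost is one derivation on laboratory and concomitant-medication data already collected. The downsides are a few lost ratings, reliance on MAR for their replacement (hence the MNAR scenario), and the fact that a positive sample does not date first use.

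For the outputs already run (18 June 2020), present this only as a labelled post hoc sensitivity analysis beside the planned primary result.
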